## 6.2 **Primary Endpoints**

The study will be considered a success if both primary effectiveness and safety objectives are met using the mITT Set at the one-sided 0.025 level of significance in the final analysis. The primary endpoint analyses will also be performed in the PP set as a supportive evidence. The primary endpoint analyses will also be performed in the mITT and PP sets by product power type (Pneumatic System and Electric System).

## 6.2.1 Primary Safety Endpoint

The primary safety endpoint is defined as freedom from a composite of new on-set major adverse events (MAE) at 30-day follow-up as adjudicated by an Independent Clinical Events Committee.

The components of the MAE are defined as:

- Cardiovascular related death: All cardiovascular cause mortality.
- Myocardial infarction (MI): Any newly diagnosed MI post procedure, defined as CK-MB ≥2X upper limit normal (ULN).
- Clinically driven target lesion revascularization (TLR): any repeat percutaneous or surgical intervention to treat objectively documented symptoms of recurrent ischemia attributable to the treated lesion.
- Clinically significant target vessel dissection: NHLBI grade C or greater as confirmed by angiography.
- Clinically significant target vessel perforation: NHLBI Type III as confirmed by angiography.
- Unplanned major target limb amputation: Amputation of the transmetatarsals or higher that was not previously planned as part of the overall treatment strategy.
- Clinically relevant distal embolization: Emboli requiring surgical or medical intervention and/or the presence of symptoms.
- Pseudoaneurysm: Disruption/weakening of the arterial wall at the treatment site as confirmed by angiography.

## 6.2.2 Analysis of Primary Safety Endpoint

The analysis of primary safety endpoint (i.e., freedom from MAE at 30 days) will be performed in the mITT analysis set. The primary safey will be assessed by calculating the proportion of subjects who have no MAE at 30 days aggregated over the mITT subjects. A 95% two-sided confidence interval will be estimated using the Clopper-Pearson interval (F-distribution method). In this analysis, the denominator includes all subjects in the mITT set and subjects who have no events but have dropped out prematurely before 30 days will be assumed not to have experienced an event.

If the lower bound of this 95% confidence interval is greater than the performance goal 85%, we can conclude the primary safety objective is met.

Each component of the primary safety endpoint will be also analyzed in the similar fashion as the aggregated primary safety endpoint in the mITT set.

Clinically-driven TLR will be analyzed on a per-subject basis. For subjects with more than one lesions, if at least one of the lesions has a clinically-driven TLR, the subject will fail the endpoint. The date of the earliest clinically-driven TLR will be used as the basis of determining a failure for the K-M analysis.

## 6.2.3 Alternative Analysis of Primary Safety Endpoint

In case of missing data of concern at 30 days when the primary safety endpoint is evaluated, the probability of a subject achieving freedom from MAE at 30 days will be estimated using Kaplan-Meier method. The standard error will be approximated using Greenwood's formula. A two-sided 95% log-log confidence interval for the probability will be constructed. The Kaplan-Meier estimate and its 95% log-log confidence interval will be constructed from the day of index procedure through the 30 days follow-up. For subjects with MAE, days of follow-up will be computed as the days from the index procedure to the onset date of the first event. For subjects without MAE, days of follow-up will be computed as the days follow-up will be computed as the days from the index procedure to the last follow-up at the time of data lock for primary analysis.

## 6.2.4 Sensitivity Analysis of Primary Safety Endpoint

A total of three sensitivity/robustness analyses will be conducted to investigate how missing data impacts the primary analysis results if missing data are of serious concern.

- 1. Complete-Case: the complete-case method uses only the subjects who have completed the 30 days follow-up or have observed the success/failure status through 30 days.
- 2. Worse-Case: all subjects who have dropped out prematurely will be assumed to have experienced an event.
- 3. A tipping-point analysis will be conducted. A tipping point is defined as the number of events in the missing cohort at which the study conclusion is changed. Let nm be the number of missing values in the mITT cohort. Starting at 0 and ending at nm, the event rate is changed by adding 1 event at a time. The 95% confidence interval will be calculated each time when adding 1 event.

## 6.2.5 Primary Effectiveness Endpoint

Primary effectiveness endpoint is technical success defined as the ability of the Cardio Flow FreedomFlowTM Orbital Circumferential Atherectomy System (Pneumatic and Electric) to achieve a residual diameter stenosis  $\leq$ 50% without adjunctive therapy, as assessed by an independent Angiographic Core Laboratory.

The primary effectiveness will be assessed by calculating the proportion of subjects who have achieved technical success over the mITT subjects. A 95% two-sided confidence interval will be estimated using the Clopper-Pearson interval (F-distribution method). If the lower bound of this 95% confidence interval is greater than the performance goal 86%, we can conclude the primary effectiveness objective is met.

## 6.2.6 Subgroup Analysis of Primary Safety and Effectiveness Endpoints

The purpose of subgroup analyses is to demonstrate the consistency of the treatment effect among the subgroups. We will use an alpha level of 0.15 to determine if there is a potential relationship between each subgroup variable of interest and the primary endpoints based on the chi-square test or Fisher's exact test. This analysis will be conducted at the subject level on the mITT analysis set. All subgroup analyses will be deemed as exploratory and we will not state any conclusions based on the subgroup analyses results.

Subgroups of interest will include smoking status (smokers vs. non-smokers), sex (male vs. female), age (below median vs. above median), race, driveshaft tip (6 Fr vs. 5 Fr), vessel size (2-2.9 mm, 3-3.9 mm, 4-4.9 mm, 5-5.9 mm, 6-6.9 mm and 7-8 mm) and product power type (Pneumatic vs. Electric).

Within each subgroup, the analysis will include the point estimate of primary effectiveness and safety endpoints and their 95% confidence intervals. The p-value that is used to compare to the PG will not be calculated and presented.

## 6.2.7 Poolability of Primary Safety and Effectiveness Endpoints

A Chi-Square test or exact text will be conducted to investigate the overall homogeneity across all sites and product power type (Pneumatic vs. Electric) for the primary safety and effectiveness endpoints. The tests will be conducted at the two-sided 0.15 level of significance. If the p-value is less than 0.15 then further evaluation is warranted. In addition, a graphical display of the proportions of primary safety and effectiveness success along with 95% confidence intervals for each site will be constructed. The confidence intervals will be constructed using the Clopper-Pearson interval (F-distribution method) and be plotted relative to the performance goal.

Sites with fewer than 5 subjects will be first combined into an adjacent single super-site that shares similar site characteristics for these analyses. The site characteristics will be determined before data lock for statistical analysis. Two sets of poolability analyses will be conducted, one is to use all sites without any combination, the other is to combine low-enrolling sites into a super-site which has similar characteristics. If the sites are not poolable, we will conduct a random effect model to determine its effect on the primary endpoints.

In addition to the homogeneity test for the primary safety and effectiveness endpoints, other variables such as baseline demographics and lesion characteristics will also be compared across sites and product power type (Pneumatic vs. Electric) to assess the appropriateness of pooling data from across all sites and product power type.

## 6.3 Secondary Endpoints

All secondary endpoints will be analyzed descriptively without hypothesis testing for all mITT patients . All secondary endpoints will also be analyzed by product power type (Pneumatic vs. Electric).

For binary variables, counts, percentages and exact 95% confidence intervals using the Clopper-Pearson method will be calculated, unless otherwise noted. For continuous variables, means, standard deviations and 95% confidence intervals will be calculated.

## 6.3.1 Clinical Success

Clinical success, defined as the ability of the FreedomFlowTM Orbital Circumferential Atherectomy System to achieve a final diameter stenosis  $\leq$ 50% immediately post treatment with or without adjunctive therapy, as assessed by an independent Angiographic Core Laboratory.

This will be reported as a binary endpoint for the mITT set, with the denominator including all subjects with evaluable angiographic data at the completion of the procedure.

## 6.3.2 Procedure Success

Procedure success, defined as  $\leq$ 50% residual stenosis at target lesion with or without adjunctive therapy, no procedure-related MAE, no device malfunction causing the procedure to be aborted. In case of having more than one target lesion, all must meet the success criteria.

Major adverse events are defined as in Section **Error! Reference source not found.** in which the primary endpoint is defined and MAEs occurring on the same day as the procedure will be assumed to have occurred during the procedure. This will be reported as a binary endpoint for the mITT set, with the denominator including all subjects with evaluable angiographic data at the completion of the procedure.

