## 5 ANALYSIS SETS

The primary analysis for effectiveness and safety will be based on a modified intent-to-treat principle. The per-protocol analysis set is designated as supportive.

Intent-to-Treat (ITT): the ITT set will be comprised of all subjects who have signed informed consent, meet all the inclusion and none of the exclusion criteria.

Modified Intent-to-Treat (mITT): the mITT set will be comprised of all ITT subjects who have the investigational device attempted.

Per-Protocol (PP): the PP set will be comprised of all subjects in the mITT set who have no major protocol deviations. All major protocol deviations will be reviewed and finalized before the data lock for final analysis.

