## 6.1.6 Missing Data

Unless otherwise specified, techniques will not be used to impute missing data. If a subject (or lesion) is missing a data point for any reason, that subject (or lesion) will not be included in that portion of the analysis. The number of data values available for each analysis will be reported so that the reader can assess the potential impact of missing data.

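### SAP 6.3.2 can drop subjects already known to be procedure failures; SAP 6.2.5 should write down how unread films and multi-lesion subjects count

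*SAP*

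**What the plan says.** **Procedure success (SAP 6.3.2).** Besides residual stenosis of 50% or less, the definition requires "no procedure-related MAE, no device malfunction causing the procedure to be aborted". For subjects with several lesions it adds: "In case of having more than one target lesion, all must meet the success criteria". The result is reported for the mITT set, "with the denominator including all subjects with evaluable angiographic data at the completion of the procedure".

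**Populations.** SAP 6.3 opens with "All secondary endpoints will be analyzed descriptively without hypothesis testing for all mITT patients". Under SAP 5, "the mITT set will be comprised of all ITT subjects who have the investigational device attempted", so a subject whose procedure was aborted after the device was attempted is in the set.

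**Technical success (SAP 6.2.5).** "The primary effectiveness will be assessed by calculating the proportion of subjects who have achieved technical success over the mITT subjects". The section does not say how a subject without a core-laboratory reading counts, and it has no rule for a subject with more than one lesion. Protocol 5.1 and 8.3 add neither.

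**General rules.** SAP 6.1.6 begins "Unless otherwise specified, techniques will not be used to impute missing data" and goes on to leave a subject with a missing value out of the analysis concerned. SAP 6.1.2 bases percentages for categorical variables on non-missing data. For primary safety, by contrast, 6.2.2 states both the denominator and the handling of dropouts, and 6.2.4 adds three missing-data analyses.

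**The concern.** Procedure success is a three-part composite, and two of its parts can settle the outcome without a film. Once a procedure-related MAE or an aborting malfunction has occurred, the subject has failed whatever the stenosis measurement would have been. Making the denominator depend on the film discards that information in one direction only: it can remove known failures, while no success is ever known without a film. The reported rate and its interval can therefore be too favourable. An aborted procedure is a natural setting for a missing final film, and one MAE component needs no film at all: "Cardiovascular related death: All cardiovascular cause mortality".

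The two points in 6.2.5 are of a different kind. They are gaps in a primary endpoint, and each would leave a choice open after the data are seen. Up to three target lesions are allowed (Protocol 6.1.1 and 6.5.1), so the lesion rule will be needed for any subject whose lesions differ in outcome.

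**Working it through.** **1. The plan's own figure.** Inputs from SAP 4 and 6.2.5: performance goal 86%, assumed rate 96%, one-sided 0.025 exact test, stated N = 101, final N = 112. The objective is met when the lower Clopper-Pearson limit exceeds 0.86.
- N = 101: 94/101 gives a lower limit of 0.8624 and passes; 93/101 gives 0.8499 and does not. So at most 7 failures pass. Error P(Bin(101, 0.14) ≤ 7) = 0.0214; power P(Bin(101, 0.04) ≤ 7) = 0.9501. Exact power stays at or above 90% from N = 100, so the stated 101 is reproduced to within one subject.
- N = 112: 104/112 gives 0.8641 and passes; 103/112 gives 0.8529 and does not. So at most 8 failures pass. Error P(Bin(112, 0.14) ≤ 8) = 0.0189; power P(Bin(112, 0.04) ≤ 8) = 0.9639.

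The sample size is not in question.

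**2. Procedure success, 6.3.2.** The documents give no count of failures or unread films. Assume 112 mITT subjects and 7 failures, of which k are known failures without an evaluable final film. The rate with all failures kept is 105/112; as written it is 105/(112 − k).

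| k dropped | Rate | Exact 95% interval |
|---|---|---|
| 0 | 105/112 = 93.8% | 0.8755 to 0.9745 |
| 1 | 105/111 = 94.6% | 0.8861 to 0.9799 |
| 2 | 105/110 = 95.5% | 0.8971 to 0.9851 |
| 3 | 105/109 = 96.3% | 0.9087 to 0.9899 |

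The overstatement runs from 0.8 to 2.6 percentage points.

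**3. An unread film in 6.2.5.** At the pass boundary one film can matter. Suppose 8 read failures and 1 unread subject among 112. Left out, 103/111 has a lower limit of 0.8629 (met). Kept as a non-success, 103/112 has 0.8529 (not met). This shows why the rule should be written down, not that the plan is biased.

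Power if unread subjects count as non-success, where a share m of true successes is unread (assumed): the failure probability becomes 0.04 + 0.96m.
- m = 1%: 0.0496; P(Bin(112, 0.0496) ≤ 8) = 0.8951.
- m = 2%: 0.0592; P(Bin(112, 0.0592) ≤ 8) = 0.7811.

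**4. The all-lesions rule in 6.2.5.** If 96% is already a per-subject rate under that rule, there is no cost. If it is a per-lesion rate, lesions are independent, and 70/20/10% of subjects have 1/2/3 lesions (all assumed), per-subject success is 0.7 × 0.96 + 0.2 × 0.96² + 0.1 × 0.96³ = 0.9448. Power at N = 112 is then P(Bin(112, 0.0552) ≤ 8) = 0.833.

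**The case against.** **Reach of 6.3.2.** The endpoint carries no hypothesis test, so the trial's success decision is untouched. Protocol 6.5.1 lists images after atherectomy, after any adjunctive or bailout intervention, and at the end of the procedure. Dissection, perforation and pseudoaneurysm are confirmed by angiography, and a subject with a later MI would normally already have a final film. What remains is mainly deaths during the procedure and some aborted cases. This stands, and it limits the size of the problem. It does not make the denominator right.

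**Conflict with 6.3.** One might infer that 6.3.2 flatly contradicts the all-mITT statement in 6.3. A specific clause that narrows a general one is ordinary drafting, so the fault does not rest on that. It lies within 6.3.2, between the definition and the denominator.

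**A partial repair is also biased.** Keeping unread known failures while dropping other unread subjects would make inclusion depend on outcome and push the rate down. This is correct, and the fix below avoids it.

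**Stronger readings of 6.2.5.** A reader might infer that excluding unread films inflates the primary error rate. The documents do not support this. The section's wording points to a full mITT denominator, 6.1.6 yields where something else is specified, and success is defined through the core laboratory's assessment. Inflation would require the general rules to override 6.2.5 and failures to go unread selectively; nothing indicates either. A reader might also fear that a subject could count as a success on any one lesion. No such rule appears anywhere, and the per-subject lesion rules in 6.2.2, 6.3.2 and 6.3.6 all fail the subject on one failed lesion.

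**Conclusion.** The denominator in SAP 6.3.2 is wrong as written: followed literally, it removes subjects already known to have failed and can only raise the reported rate. The effect is confined to a descriptive secondary endpoint and probably to few subjects. Under the assumed 7 failures in 112, with 1 to 3 lacking an evaluable final film, it is 0.8 to 2.6 points.

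The unread-film question in 6.2.5 is largely answered by the section's own wording and needs only to be made explicit. The missing lesion rule is a genuine omission in a primary endpoint, but no bias is shown. Both should be closed before database lock so that neither is chosen with the data in view. All counts of unread films and multi-lesion subjects used here are assumptions; the documents give none.

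**What to change.** **SAP 6.3.2.** Use all mITT subjects as the denominator. Count a procedure-related MAE or an aborting device malfunction as a failure whether or not the final film is evaluable. Show separately the subjects who cannot be classified (no evaluable film and no known failure), and report the rate with them counted as failures and again as successes.

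**SAP 6.2.5.** State that all mITT subjects stay in the denominator and that the non-missing rules in both 6.1.2 and 6.1.6 do not apply; naming only one would leave the other open. State how a subject without a core-laboratory reading counts, and add a tipping-point analysis like the one in 6.2.4.

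**Lesion rule.** Carry the all-lesions rule of 6.3.2 into 6.2.5 and 6.3.1. The evaluable-film denominator of 6.3.1 does not share the fault above, because clinical success is purely angiographic.

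**Cost.** The 6.3.2 change is wording plus one table. The 6.2.5 choices can cost power, starting from 96.4% at N = 112. Counting unread films as non-success brings it to 89.5% or 78.1% if 1% or 2% of true successes are unread, so missing readings should be queried before lock. The all-lesions rule brings it to about 83% if 96% is a per-lesion rate, lesions are independent, and 70/20/10% of subjects have 1/2/3 lesions. It costs nothing if 96% is already per subject under that rule. The SAP should say which is meant. The two costs were computed separately; together they would be larger.

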## 6.3.3 Change in Ankle-Brachial Index (ABI)

Change in ankle-brachial index (ABI) from pre-procedure (i.e., baseline) to 30 days and 6 months.

The endpoint will be summarized for the mITT set. Within-subject changes will be calculated as visit value minus baseline value such that a negative change reflects a deterioration and a positive change signifies an improvement. Summaries of improved/same/worsened will be provided along with continuous summaries.

## 6.3.4 Change in Rutherford Classification

Change in Rutherford classification from pre-procedure (i.e., baseline) to 30 days and 6 months.

The endpoint will be summarized for the mITT set. Within-subject changes will be calculated as visit value minus baseline value such that a negative change reflects an improvement and a positive change signifies a deterioration. Summaries of improved/same/worsened will be provided alongside the ordinal summaries.

## 6.3.5 Change in Patient Reported Outcomes (PRO)

Change in patient reported outcomes (PRO, VascuQoL questionnaire) at 30 days and 6 months.

The total score and subdomain score will be summarized for the mITT set. Within-subject changes will be calculated as visit value minus baseline value such that a positive change reflects an improvement and a negative change signifies a deterioration. Summaries of improved/same/worsened will be provided alongside the continuous summaries.

## 6.3.6 Rate of Clinically-Driven Target Lesion Revascularization

Rate of clinically-driven target lesion revascularization (TLR) at 30 days and 6 months.

Clinically-driven TLR will be adjudicated by the CEC. The date of the clinically-driven TLR will be determined from the revascularization date reported on the site-reported form corresponding to the site-reported adverse event that the CEC adjudicated as a clinically-driven TLR.

Clinically-driven TLR will be analyzed on a *per-subject* basis. For subjects with more than one lesions, if at least one of the lesions has a clinically-driven TLR, the subject will fail the endpoint. The date of the earliest clinically-driven TLR will be used as the basis of determining a failure for time to event analysis in Section 6.1.5. The rates at 30 days and 6 months will be estimated for the mITT set from a Kaplan-Meier analysis.

## 6.3.7 Rate of Clinically-Driven Target Vessel Revascularization

Rate of clinically-driven target vessel revascularization (TVR) at 30 days and 6 months (as assessed by an independent Angiographic Core Laboratory).

Events categorized as a clinically-driven TVR by the CEC will meet the criteria for this endpoint. The date of the clinically-driven TVR will be determined from the revascularization date reported on the site-reported target vessel revascularization form corresponding to the site-reported adverse event corresponding to the CEC adjudication.

Clinically-driven TVR will be analyzed on a *per-subject* basis. The rate at 30 days and 6 months will be estimated for the mITT set from a Kaplan-Meier analysis according to Section **Error! Reference source not found.** 

## 6.3.8 Primary Patency, Primary Assisted Patency and Secondary Patency

Primary patency, primary assisted patency and secondary patency will be derived on a *per-lesion* level.

Primary patency is defined as the absence of target lesion restenosis evaluated by duplex ultrasound (i.e., peak systolic velocity ratio  $[PSVR] \le 2.5$ ) and freedom from clinically-driven target lesion revascularization. The primary patency success must meet success criteria for the both components of patency. If the lesion fails either component of the patency endpoint, the lesion will be considered a failure for the efficacy endpoint.

Primary assisted patency is defined as patency of the target lesion following endovascular reintervention at the target vessel site in case of symptomatic restenosis. This is a cumulative

patency rate including patent target lesion post re-intervention for restenosis at the given followup timepoint.

Secondary patency reports patency of the target lesion after treatment of a (re)occlusion of the index lesion. This is a cumulative patency rate, including re-intervention (restenosis or re-occlusion) at the given follow-up timepoint.

A Kaplan-Meier (KM) survival analysis as described in Section 6.1.5 will be used to estimate the patency rates including primary, primary asissted and secondary. The patency rates will be presented as the KM estimate of freedom from loss of patency at 30 days and 180 days post-procedure. The survival curves, the KM estimate, and the 95% confidence interval will be presented. Lesions will be censored at the day of last subject follow-up for the following senarios:

- Have 6 months follow-up but no analyzable duplex ultrasound data, and no clinicallydriven TLR
- Have no 6 months follow up but also have no event of interst.

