6.1.1 Inclusion Criteria

Subjects must meet ALL of the following criteria to be eligible for participation in the study:

- 1. Age \geq 18 years old.
- 2. Subject is a candidate for percutaneous endovascular intervention for peripheral vascular disease in the lower extremity.
- 3. Objective hemodynamic evaluation that subject has a resting ankle-brachial index (ABI) $\leq 0.90 \text{ } \underline{\textbf{OR}}$ a resting toe-brachial index (TBI) of $\leq 0.80 \text{ } \underline{\textbf{OR}}$ ankle pressure of $\leq 70 \text{ mmHg}$.
- 4. Clinical presentation of lifestyle limiting claudication, rest pain and/or ischemic wound as characterized by Rutherford Classification 2, 3, 4, or 5.
- 5. Disease is located in the common femoral, superficial femoral, popliteal, tibioperoneal, anterior tibial, posterior tibial, or peroneal arteries.
 - a. De novo target lesion(s) with stenosis \geq 70% by visual estimation and/or
 - b. Lesion(s) treated by percutaneous transluminal angioplasty (PTA) and/or atherectomy ≥ 3 months prior with a restenosis ≥70% by visual estimation.
 - c. Up to three lesions can be treated at the index procedure provided the cumulative total lesion length is ≤ 20 cm AND all lesions are in the same target leg.
- 6. Target reference vessel diameter (proximal and distal to target lesion) is 2 to 8 mm by angiographic visual estimation.
- 7. At least one patent vessel run-off to the ankle or foot at baseline.
- 8. The target lesion(s) can be successfully crossed with a commercially available 0.014" atherectomy guidewire without any complications during wiring procedure.
- 9. Subject signs a written Informed Consent form to participate in the study, prior to any study mandated determinations or procedure.

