## 6.1.5 Kaplan-Meier Analysis

For time to event endpoints analyzed with a Kaplan-Meier method, analysis time points will be presented at 30 and 180 days. Unless otherwise specified, if a subject is event-free, their date of censoring will be considered as the date of last contact in the study. For Kaplan-Meier estimates presented with the corresponding 95% log-log confidence interval  $(L_{\hat{s}}, U_{\hat{s}})$ , Greenwood's estimate of the standard error will be used. The Kaplan-Meier estimate of the event rate,  $\hat{F}$ , may be computed as  $1 - \hat{S}$  and the corresponding 95% log-log confidence interval is as follows:

$$L_{\hat{F}} = 1 - U_{\hat{S}} \\ U_{\hat{F}} = 1 - L_{\hat{S}}.$$

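### Per-lesion patency intervals use Greenwood's standard error although one subject can contribute up to three lesions, so they are too narrow if outcomes within a subject are positively correlated

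*SAP*

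**What the plan says.** - **Unit of analysis.** SAP 6.3.8: "Primary patency, primary assisted patency and secondary patency will be derived on a *per-lesion* level".
- **Estimator and interval.** SAP 6.3.8: "A Kaplan-Meier (KM) survival analysis as described in Section 6.1.5 will be used to estimate the patency rates", and "The survival curves, the KM estimate, and the 95% confidence interval will be presented".
- **Standard error.** For log-log 95% intervals, SAP 6.1.5 says: "Greenwood's estimate of the standard error will be used". The same section fixes the times: "analysis time points will be presented at 30 and 180 days".
- **Lesions per subject.** Protocol 6.1.1, inclusion criterion 5c: "Up to three lesions can be treated at the index procedure", provided that all are in the same leg and their total length is at most 20 cm. Protocol 6.5.1 repeats the limit of three.
- **Role and breakdown.** SAP 6.3: "All secondary endpoints will be analyzed descriptively without hypothesis testing", and "All secondary endpoints will also be analyzed by product power type".

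Neither document provides a cluster-robust variance, subject-level resampling, a frailty model or a per-subject patency rule. The one random-effect model in the SAP (6.2.7) concerns sites and the primary endpoints.

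**The concern.** Greenwood's formula assumes independent units. Lesions treated in one leg share the subject's risk factors, the operator, the device and the run-off, so a positive correlation of their outcomes is plausible. Each additional lesion in a subject then carries less information than the formula credits to it, and the interval is too short.

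The SAP deals with multiple lesions elsewhere. Clinically driven TLR (6.3.6) is counted per subject, with one failed lesion failing the subject. TVR (6.3.7) is per subject, and procedure success (6.3.2) needs every target lesion to succeed. Patency alone uses the lesion as the unit and keeps a variance for independent units.

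At stake is the precision shown for three patency definitions × two time points × three groups (overall, pneumatic, electric) = 18 intervals labelled 95%. With no test planned, the estimate and its interval are the whole reported result for this endpoint.

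**Working it through.** The documents state no patency rate, lesion mix, correlation or interval width, so there is no planned figure to reproduce. Everything beyond the 112 subjects (about 56 per power type) and the 10% dropout is an assumption.

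**1. Formula.** Let m be the number of lesions in a subject and ICC the correlation of patency status between two lesions of one subject. Without censoring, Kaplan-Meier at a fixed day is a simple proportion and Greenwood's variance is the binomial variance. Then

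true SE / Greenwood SE = √(1 + ICC × (E[m²]/E[m] − 1)),

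whatever the patency level.

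Assumed shares of subjects with 1/2/3 lesions:

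- 82/15/3%: E[m] = 0.82 + 0.30 + 0.09 = 1.21; E[m²] = 0.82 + 0.60 + 0.27 = 1.69; factor 1.69/1.21 − 1 = 0.397.
- 65/25/10%: E[m] = 1.45; E[m²] = 2.55; factor 0.759.
- 50/30/20%: E[m] = 1.70; E[m²] = 3.50; factor 1.059.

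Example: mean 1.21 and ICC 0.3 give √(1 + 0.3 × 0.397) = √1.119 = 1.058.

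| Mean lesions | ICC 0 | ICC 0.1 | ICC 0.3 | ICC 0.7 (stress case) |
|---|---|---|---|---|
| 1.21 | 1.000 | 1.020 | 1.058 | 1.130 |
| 1.45 | 1.000 | 1.037 | 1.108 | 1.237 |
| 1.70 | 1.000 | 1.052 | 1.148 | 1.320 |

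**2. Half-widths at 75% patency.** These use 1.96 × √(0.75 × 0.25 / lesions), without censoring. The log-log interval is slightly asymmetric.

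- 112 subjects, mean 1.21: 112 × 1.21 = 135.5 lesions; planned half-width 7.3 points; needed at ICC 0.3: 7.3 × 1.058 = 7.7.
- 112 subjects, mean 1.70: 190.4 lesions; planned 6.2; needed at ICC 0.3: 7.1; at ICC 0.7: 8.1.
- 56 subjects, mean 1.21: 67.8 lesions; planned 10.3; needed at ICC 0.3: 10.9.
- 56 subjects, mean 1.70: 95.2 lesions; planned 8.7; needed at ICC 0.7: 11.5.

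Simulations with 10% dropout agree closely. In the mild case with 112 subjects (mean 1.21, ICC 0.3), the planned half-width is 7.4 to 7.5 and the needed one 7.8 to 8.0. In the stress case (mean 1.70, ICC 0.7), the figures are 6.3 and 8.2.

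**3. Coverage of the planned interval.** Set-up: Kaplan-Meier at day 180, Greenwood SE, log-log interval, 112 subjects, true patency 75%, exponential failure times, Gaussian copula matched to the day-180 ICC, 10% of subjects dropping out with all their lesions censored together, 10,000 trials per cell.

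| Mean lesions | ICC 0 | ICC 0.1 | ICC 0.3 | ICC 0.7 |
|---|---|---|---|---|
| 1.21 | 95.1% | 94.9% | 93.4% | 92.1% |
| 1.45 | 94.9% | 94.5% | 92.4% | 89.2% |
| 1.70 | 95.4% | 93.7% | 91.3% | 87.3% |

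Simulated SE ratios lie within 0.02 of the formula. With 56 subjects, coverage runs from 95.5% down to 86.8%. An interval clustered on subject covers 94.4% to 95.3% in every cell at both sizes. At ICC 0, shared censoring leaves coverage at about 95%, so it is not a cause.

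**4. Other settings.** At 80% patency, with 1/2/3 shares of 85/12/3, 70/20/10 and 50/30/20% and a correlation of 0.5 on the copula's latent scale (not the same as the ICC above), SE ratios were 1.07, 1.10 and 1.13 and coverage was 93.6%, 92.4% and 91.8% (2,000 runs each). A beta-binomial check at 90% patency with 112 subjects gave coverage from about 95.5% at ICC 0 to 86.8% in the most extreme cell.

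**The case against.** - **It is only descriptive.** This is true. SAP 6.2 rests study success on the two primary endpoints alone. That limits the consequence but does not make the intervals right.
- **The effect may be negligible.** This is also true under some assumptions. With a mean of 1.21 lesions and ICC 0.1, coverage is 94.9%; with one lesion per subject, Greenwood is exactly the right choice. Lesions in one subject may span femoropopliteal and lower-leg arteries, where Protocol 1 says results differ, so a strong correlation cannot be presumed. The ICC 0.7 figures are a stress case and not an expectation.
- **The 30-day intervals may behave differently.** This stands in part. At an assumed 95% patency the standard error is still 4% to 17% too small. Coverage depends on the lesion mix: in the mildest one (112 subjects, ICC 0.1 to 0.3) the planned interval covers 95.7% to 96.2%, while at mean 1.70 and ICC 0.3 it covers 92.2%. At an assumed 98% with 56 subjects, 16% to 28% of simulated trials have no event, and neither interval can be computed.
- **The simulation is stylised.** It uses exponential failure times and one generic patency outcome, whereas restenosis is found by duplex at two visits. That stands, but the SE ratio in step 1 does not depend on the timing model.
- **The SAP already has a route.** SAP 6.1.6 reports the number of values in each analysis, and 6.6 allows documented changes if assumptions fail. Neither shows the distribution of lesions per subject or prespecifies a variance.

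**Conclusion.** The concern holds. As written, the rule applies a variance for independent units to lesions that may be clustered in subjects, and the intervals are too narrow whenever some subjects have more than one lesion and their outcomes are positively correlated.

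The direction is firm under that condition; the size is not, because it rests on an assumed lesion mix, correlation and patency rate. For the mixes considered and an ICC of 0.1 to 0.3, the day-180 standard error should be 2% to 15% larger, and coverage at 75% patency and 112 subjects is about 95% to 91% instead of 95%. The coverage figures should not be carried over to day 30. The point estimates, the primary endpoints, the sample size and the success rule are untouched. The correction is worth making but does not bear on the trial's conclusion.

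**What to change.** Keep the per-lesion Kaplan-Meier estimate and add to SAP 6.3.8:

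> Because a subject may contribute up to three lesions, the 95% log-log interval for each patency estimate will use a variance clustered on subject (or a bootstrap that resamples subjects) in place of Greenwood's formula. The number of subjects with one, two and three target lesions will be reported overall and by power type.

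The SAP should name one of the two methods before database lock, so that the variance is not chosen after the data are seen. Subject-level patency (all treated lesions patent) could be added, but it is a different estimand and is not needed for this correction.

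The cost is two sentences and a few lines of code, with no new data. The intervals become slightly wider if correlation is present, and nothing is gained if nearly all subjects turn out to have a single lesion.
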